5.2.2.1 Management of stomatitis, oral mucositis, and mouth ulcers

Patients with a clinical history of stomatitis/mucositis/mouth ulcers and those with gastrointestinal morbidity associated with mouth/dental infections, irritation of esophageal mucosa e.g. gastroesophageal reflux disease (GERD) and pre-existing stomatitis/mucositis must be monitored even more closely. Patients should be instructed to report the first onset of buccal mucosa irritation/reddening to their study physician immediately.

Mouth ulcers, stomatitis and oral mucositis have been seen in patients treated with everolimus. Stomatitis/oral mucositis/mouth ulcers due to everolimus should be treated using local supportive care. If examination reveals mouth ulcers rather than a more general inflammation of the mouth,

please classify the adverse event as such. Please follow the paradigm below for treatment of stomatitis/oral mucositis/mouth ulcers (**Table 5-4**):

1. For mild toxicity (grade 1) no dose adjustment required; use conservative measures such as **non-alcoholic mouth wash or salt water (0.9%) mouth wash** several times a day until resolution.
2. For more severe toxicity (grade 2 in which case patients have pain but are able to maintain adequate oral alimentation, or grade 3 in which case patients cannot maintain adequate oral alimentation), the suggested treatments are **topical analgesic mouth treatments (i.e., local anesthetics such as benzocaine, butyl aminobenzoate, tetracaine hydrochloride, menthol, or phenol)** with or without **topical corticosteroids**, such as triamcinolone oral paste 0.1% (Kenalog in Orabase®).
3. Agents containing hydrogen peroxide, iodine, and thyme derivatives may tend to worsen mouth ulcers. It is preferable to avoid these agents.
4. Antifungal agents must be avoided unless a fungal infection is diagnosed. In particular, systemic imidazole antifungal agents (ketoconazole, fluconazole, itraconazole, etc.) should be avoided in all patients due to their strong inhibition of everolimus metabolism, therefore leading to higher everolimus exposures. Therefore, topical antifungal agents are preferred if an infection is diagnosed. Similarly, antiviral agents such as acyclovir should be avoided unless a viral infection is diagnosed.

Table 5-4: Management of oral mucositis (stomatitis) associated with everolimus.

Severity	Everolimus Dose Adjustment and Management Recommendations (see 4.2)
Grade 1 (Minimal symptoms, normal diet)	No dose adjustment required. Manage with non-alcoholic or salt water (0.9%) mouth wash several times a day.
Grade 2 (Symptomatic but can eat and swallow modified diet)	- Temporary dose interruption until recovery to grade ≤1. Re-initiate everolimus at the same dose. - If stomatitis recurs at grade 2, interrupt dose until recovery to grade ≤1. Re-initiate everolimus at a lower dose (for this trial if it was 2.5mgs, then therapy will be discontinued). Manage with topical analgesic mouth treatments (e.g. benzocaine, butyl aminobenzoate, tetracaine hydrochloride, menthol or phenol) with or without topical corticosteroids (i.e. triamcinolone oral paste).
Grade 3 (Symptomatic and unable to adequately eat or hydrate orally)	Temporary dose interruption until recovery to grade ≤1. Re-initiate everolimus at lower dose (for this trial if it was 2.5mgs, then therapy will be discontinued). Manage with topical analgesic mouth treatments (i.e. benzocaine, butyl aminobenzoate, tetracaine hydrochloride, menthol or phenol) with or without topical corticosteroids (i.e. triamcinolone oral paste)*
Grade 4 (Symptoms associated with life-threatening consequences)	Discontinue everolimus and treat with appropriate medical therapy.

5.2.2.2 Management of Hyperlipidemia and Hyperglycemia

Treatment of hyperlipidemia should take into account the pre-treatment status and dietary habits. Blood tests to monitor hyperlipidemia must be taken in the fasting state. Grade 2 or higher hypercholesterolemia (>300 mg/dL or 7.75 mmol/L) or grade 2 hypertriglyceridemia or higher (>2.5x upper normal limit) should be treated with a 3-hydroxy-3-methyl-glutaryl (HMG)-CoA reductase inhibitor (e.g. atorvastatin, pravastatin, fluvastatin) or appropriate triglyceride-lowering medication, in addition to diet. Note: Concomitant therapy with fibrates and an HMG-CoA reductase inhibitor is associated with an increased risk of a rare but serious skeletal muscle toxicity manifested by rhabdomyolysis, markedly elevated creatine phosphokinase (CPK) levels and myoglobinuria, acute renal failure and sometimes death. The risk versus benefit of using this therapy should be determined for individual patients based on their risk of cardiovascular complications of hyperlipidemia.

Dyslipidemia (including hypercholesterolemia and hypertriglyceridemia) has been reported in patients taking everolimus. Monitoring of blood cholesterol and triglycerides prior to the start of everolimus therapy and periodically thereafter as well as management with appropriate medical therapy is recommended. Hyperglycemia has been reported in patients taking everolimus. Monitoring of fasting serum glucose is recommended prior to the start of Everolimus and periodically thereafter. More frequent monitoring is recommended when everolimus is co-administered with other drugs that may induce hyperglycemia. Optimal glycemic control should be achieved before starting a patient on Everolimus. Hyperlipidemia and hypertriglyceridemia should be treated according to local best clinical practice (**Table 5-5**). Patients should be monitored clinically and through serum biochemistry for the development of rhabdomyolysis and other adverse events as required in the product label/data sheets for HMG-CoA reductase inhibitors (statins).

Table 5-5. Management of hyperlipidemia/hypertriglycemia associated with everolimus

Severity	Everolimus Dose Adjustment and Management Recommendations
Grade 1	No dose adjustment required. Initiate appropriate medical therapy and monitor.
Grade 2	No dose adjustment required. Manage with appropriate medical therapy and monitor.
Grade 3	Temporary dose interruption. Re-initiate everolimus at lower dose (for this trial if it was 2.5mgs, then therapy will be discontinued). Manage with appropriate medical therapy and monitor.
Grade 4	Discontinue everolimus and treat with appropriate medical therapy.

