5.2.2.7 Renal Failure Events

Cases of renal failure (including acute renal failure), some with fatal outcome, occurred in patients treated with everolimus. Renal function of patients should be monitored particularly where patients have additional risk factors that may further impair renal function. Elevations of serum creatinine, usually mild, and proteinuria have been reported in patients taking everolimus. Monitoring of renal function, including measurement of blood urea nitrogen (BUN), urinary protein, or serum creatinine, is recommended prior to the start of everolimus therapy and periodically thereafter.

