5.4.2 Treatment Phase

The following evaluations and procedures will be performed during the **treatment phase**: (All assessments should be performed within 5 working days of the protocol-specified date).

- Physical examination, vital signs, weight, and performance status on weeks 4, 8, 12, 16, 20 and 24.
- Laboratory assessments: CBC with differential and platelet count, serum chemistries (glucose, BUN, creatinine, total protein, albumin, bilirubin, calcium, alkaline phosphatase, AST, and ALT), and serum electrolytes (Na, K, Cl) on week 1 and at the beginning of each cycle until week 24.
- Lipid panel (cholesterol, triglycerides, HDL, and LDL) in a fasting state (at least 8 hours) should be obtained at least on cycle 2 and, if elevated, repeated on each cycle until recovery to baseline value or grade 1 (see 5.2.2.2 for management of hyperlipidemia and hyperglycemia).

Serum estradiol levels on weeks 4, 12, and 20 in women receiving goserelin.

- Hepatitis panel as clinically indicated.
- Research biopsy (core needle biopsy of the tumor) at week 4 (required).
- Tumor assessments: Ultrasound of the breast will be obtained on week 4, 8, 12, 16, 20 and 24. Mammogram will be obtained on week 24. Additional PET scans or CT of the chest, abdomen, and pelvis, or bone scans are not required during treatment phase except as clinically indicated (see section **7.2 Measurement of Effect**). MRI breast will be obtained at baseline, week 12 and 24.
- Evaluation of the ejection fraction with an echocardiogram/MUGA only as clinically indicated.
- Surgical evaluation at the end of neoadjuvant therapy. **There must be at least 4 weeks between the last dose of everolimus and TRC105 and surgery.** Patients will continue letrozole until the day before surgery.
- Concomitant medication assessment.
- Assessment of adverse events.

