5.4.3 Safety Follow-up Phase

Patients will complete participation in the protocol at the time of surgery and will not be followed unless the patient requires follow up of adverse events. The following evaluations and procedures will be performed at **early termination**. Every effort should be undertaken for the following procedures to be completed within 10 days.

- Clinical evaluations: Weight, physical examination (complete), vital signs and performance status. There must be a complete and clear documentation of objective response or disease progression using the RECIST criteria. Reason(s) for discontinuation must be documented.
- Laboratory assessment: UA, CBC with differential and platelet count, serum chemistries (glucose, BUN, creatinine, total protein, albumin, bilirubin, calcium, alkaline phosphatase, AST, and ALT), serum electrolytes (Na, K, Cl), and lipid panel (cholesterol, triglycerides, HDL, and LDL) in a fasting state (at least 8 hours).
- Tumor assessments: Mammogram, breast ultrasound, and breast MRI. Spiral CT scans of chest, abdomen, and pelvis, bone scan, and any other procedure are not required per protocol but will be obtained if clinically indicated.
- Concomitant medication assessment.
- Assessment of adverse events. If the patient has an ongoing toxicity, the patient should be followed until resolution or stabilization. Serious and non-serious adverse events occurring

within 30 days of day 0 of the last treatment should be reported on the appropriate adverse event CRF.

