7.2.1 Antitumor Effect

Response and progression will be evaluated in this study using the new international criteria proposed by the Response Evaluation Criteria in Solid Tumors (RECIST)¹¹⁸ Committee (http://ctep.cancer.gov/protocolDevelopment/docs/recist_guideline.pdf)¹¹⁸. Changes in only the largest diameter (one-dimensional measurement) of the tumor lesions are used in the RECIST criteria.

Table 7-1: Study Calendar (see 5.4 Study Procedures)

	SC	Treatment Phase ^{11, 13}												End of treatment ⁷	Follow up	
		C1D1	C1D4	C1D15	C2D1	C2D15	C3D1	C3D15	C4D1	C4D15	C5D1	C5D15	C6D1			C6D15
Informed consent	X															
Demographics	X															
Inclusion/Exclusion	X															
Past Medical History	X															
History Present Illness	X															
Concurrent Medications		X-----X														
Prior therapy	X															
Physician Visits	X	X			X		X		X		X		X		X	X
Physical Examination	X	X			X		X		X		X		X		X	X
Performance status	X	X			X		X		X		X		X		X	X
Vital Signs	X	X			X		X		X		X		X		X	X
Height/Weight	X	X			X		X		X		X		X		X	X
CBC and differential	X		X		X		X		X		X		X		X	X
Chemistries/Electrolytes	X		X		X		X		X		X		X		X	X
FSH, LH,estradiol levels	X															
Estradiol levels ¹⁵					X				X				X			
Pregnancy test ¹⁴	X															
Lipid panel ¹	X				X											
Hepatitis panel ²	X															
Urinalysis ³	X															
12-lead EKG	X															
Serum ferritin level	X															
Everolimus serum level		X ¹⁰			X ¹⁰											
TRC105 serum level		X ¹⁰			X ¹⁰											
Anti-TRC105 antibodies (APA) ¹¹		X			X		X		X		X		X			X ¹¹
VEGF-A serum ¹²	X			X	X											X
sEng / TGF-β serum ¹²	X			X	X											X
Angiopoietin-1/2 serum ¹²	X			X	X											X
Research Biopsy ⁴	X				X											X
Adverse Events		X-----X														

Mammography	X														X	
Breast ultrasound	X				X		X		X		X		X		X	
Breast MRI ⁵	X								X						X	
Body CT/MRI/PET ⁶	(X)															
Letrozole ⁸	X-----X															
Everolimus ⁹	X-----X															
TRC105 ⁹		X	X	X	X	X	X	X	X	X	X	X	X	X	X	
Goserelin ¹³		X			X		X		X		X		X			
Surgery															X	

Notes:

1. Cholesterol, triglycerides, HDL, and LDL in a fasting state (8 hours) should be obtained at least on cycle 2 and, if elevated, repeat on each cycle until recovery to baseline value or grade 1.
2. Hepatitis panel should be obtained on screening and repeated as clinically indicated (HBV-DNA, HBsAg, HBs Ab, and HBc Ab, and RNA-PCR).

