3. Urinalysis should be obtained on screening and repeated as clinically indicated.
4. Research biopsy (core needle biopsy of the tumor).
5. Breast MRI is required by the protocol.
6. As clinically indicated after baseline diagnosis.
7. Within a week of surgery.
8. Continuation until the day prior to surgery.
9. Continuation no later than 4 weeks prior to surgery.
10. Samples will be collected and concentrations of the agents measured on cycles 1 and 2 at the following time points: pre-dose, 1, 2, 4, 6, and 24, hours, and cycle 1 day 4 pre-dose.
11. TRC105 anti-product antibodies (APA) will be collected before dosing on cycle 1 day 1, every 4 weeks thereafter, 4 and 12 weeks following the last dose of TRC105.
12. Markers of angiogenesis (VEGF-A, soluble VEGFR2, activin A and activin B, angiopoietin-1 and -2, TGF- β , soluble endoglin) will be measured on samples collected pre-dose, cycle 1 day 15, cycle 2 day 1, and prior to surgery.
13. Administered only if FSH, LH, and estradiol NOT within postmenopausal range at the time of enrollment.
14. In women with childbearing potential
15. Only in women receiving goserelin

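### Only one on-treatment lipid panel is fixed for every patient, and only early terminators have listed exit lipid and urine tests, so lipid adverse-event rates may be understated and are unevenly ascertained

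*Combined protocol and SAP*

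**What the plan says.** **Lipids.** Section 5.2.2.2 recommends "Monitoring of blood cholesterol and triglycerides prior to the start of everolimus therapy and periodically thereafter" and gives no interval. Section 5.4.2 says the fasting panel "should be obtained at least on cycle 2 and, if elevated, repeated on each cycle until recovery to baseline value or grade 1". Table 7-1 marks the panel at screening and cycle 2 day 1 only, and its note 1 repeats the rule: "should be obtained at least on cycle 2 and, if elevated, repeat on each cycle until recovery to baseline value or grade 1".

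**Urine.** Table 7-1 note 3 reads "Urinalysis should be obtained on screening and repeated as clinically indicated". Section 5.4.2 lists no urinalysis. Section 5.2.2.7 names BUN first among its renal measures and continues "urinary protein, or serum creatinine, is recommended prior to the start of everolimus therapy and periodically thereafter".

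**Exit tests.** For early termination, section 5.4.3 lists "Laboratory assessment: UA, CBC with differential and platelet count, serum chemistries" and, in the same item, "and lipid panel (cholesterol, triglycerides, HDL, and LDL) in a fasting state (at least 8 hours". Section 7.1 says that patients who complete treatment and go to surgery need no end-of-treatment visit. Table 7-1 nonetheless has an end-of-treatment column. It marks blood count and chemistries but neither lipids nor urinalysis, and note 7 places it within a week of surgery.

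**Use of the data.** Section 1.2.1 makes adverse-event rates part of the primary endpoint. Section 8.1 counts laboratory abnormalities that qualify as adverse events. Section 10.2 estimates the rates as simple proportions with exact 95% intervals, in everyone who received at least one dose.

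**The concern.** A rate built from laboratory values depends on when the laboratory looks. The repeat rule follows an abnormality that has already been found. It does not find a first rise after a normal cycle 2 panel, and it ends once the value is back to baseline or grade 1. Lipid rises rarely cause symptoms that would prompt a test, so little else would reveal a late onset.

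Three features of the plan make this matter:

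- The primary objective is tolerability over 24 weeks. Section 4.4 itself doubts that six months can be given without dose reductions, delays or interruptions, since the cited experience is four months. The later weeks are where this trial adds information.
- Lipid events are expected. Section 5.2.2 cites hypercholesterolemia in 16.1% on letrozole plus everolimus against 6.1% on letrozole, and section 8.2.2 lists raised cholesterol and triglycerides as very common.
- Table 5-5 ties management to lipid grade. After a normal cycle 2 panel, a new grade can be known only from an unscheduled test.

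The exact interval in section 10.2 covers sampling error only; it does not allow for events that were never looked for.

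**Working it through.** No sample size, error rate or stated figure in the plan depends on this schedule, so there is no plan figure to reproduce. The check is a count of fixed tests, followed by an illustration of what the gap could mean.

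**Step 1. Count the tests** (sections 5.4.1, 5.4.2, 5.4.3 and 7.1; Table 7-1 with notes 1 and 3).

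| Test | Screening | Fixed on treatment | Exit, early terminator | Exit, completer | Conditional |
|---|---|---|---|---|---|
| Fasting lipids | 1 | 1 (C2D1) | 1 | 0 | each cycle if elevated |
| Urinalysis | 1 | 0 | 1 | 0 | if clinically indicated |

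**Step 2. Unobserved time.** Treatment lasts 24 weeks, in six 4-week cycles (section 4.3). Cycle 2 day 1 falls at week 4. For a patient normal then, the time without a fixed lipid test is (24 − 4)/24 = 20/24 = 83%.

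**Step 3. Share of cases the cycle 2 panel could see.** The documents give no onset times, so this step rests on assumptions: an abnormality persists once present, and no unscheduled or exit test is done.

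- *All onset by week 4:* the share seen is 100% and nothing is missed.
- *Constant hazard:* with true 24-week risk p, risk by week 4 is 1 − (1 − p)^(4/24). For p = 5% this is 0.85%, a share of 0.170. For p = 20% it is 3.65%, a share of 0.183. For p = 40% it is 8.16%, a share of 0.204. The share is therefore about 17% to 20%.
- *In between:* if the true 24-week rate were 20% and three-quarters, half or one-quarter of onsets fell by week 4, the panel would show 15%, 10% or 5%.

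**Step 4. Illustration with the cited rate.** The 16.1% comes from a trial of about 4 months, taken here as 16 weeks. Under a constant hazard:

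- by week 4: 1 − 0.839^(4/16) = 4.3%
- by week 24: 1 − 0.839^(24/16) = 23.2%
- share seen: 0.0429/0.2315 = 0.185

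For the 26 to 38 patients planned in section 4.3, that is 26 × 0.0429 = 1.1 against 26 × 0.2315 = 6.0 patients, and 38 × 0.0429 = 1.6 against 38 × 0.2315 = 8.8. These counts illustrate the mechanism. They do not predict this three-drug regimen.

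**Step 5. Where an exit test would have to sit.** Section 5.4.2 requires at least 4 weeks between the last everolimus dose and surgery. The Table 7-1 end-of-treatment visit is within a week of surgery, so it falls at least 4 − 1 = 3 weeks after the last dose. With the 30-hour half-life in section 5.2.2, that is (21 × 24)/30 = about 17 half-lives. Early-termination tests are targeted within 10 days (section 5.4.3). Adding lipids to the existing end-of-treatment column would therefore not give completers a comparable test.

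**The case against.** The best defence is that section 5.2.2.2 only recommends monitoring, without an interval, and that the schedule sets a floor with mandatory repeats when a value is raised. On that view the sections do not strictly conflict. This stands as far as it goes: one panel is the minimum, and nothing bars more. It does not answer the gap, because neither the floor nor the repeat rule looks for late first onset.

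Several stronger readings are tempting, and the documents do not support them:

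- *That the rates are understated.* Missed tests can only lower an observed rate, so the direction is clear. Whether any shortfall occurs, and how large, depends on onset timing and unscheduled testing, which are not given.
- *That events would be counted mainly in early stoppers.* Take the cited 18.8% discontinuation and 16.1% event rates in 20 patients. Then 20 × 0.188 = 3.8 stop early and 16.2 complete. With onset uniform over 24 weeks, the cycle 2 panel finds 16.2 × 0.161 × 4/24 = 0.43 case among completers. Early stoppers yield at most 3.8 × 0.161 = 0.61, and 0.31 if they stop at week 12 on average. If half of onsets fall by week 4, completers yield 16.2 × 0.161 × 0.5 = 1.3. Ascertainment is uneven, but a predominance of early stoppers does not follow. Section 10.2 also plans no analysis relating stopping to toxicity.
- *That the urinalysis schedule contradicts section 5.2.2.7.* That section joins BUN, urinary protein and creatinine with an or, and section 5.4.2 draws BUN and creatinine each cycle. The recommendation is met; only the uneven exit urinalysis remains.
- *That dose selection is affected through lipids.* The MTD rests on first-cycle DLTs (section 4.1.3), and the cycle 2 day 1 panel falls at the end of that window.
- *That Table 5-5 cannot be triggered after week 4.* It can, through an unscheduled test.

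**Conclusion.** The point holds as a weakness in ascertainment. Every patient has one fixed on-treatment lipid panel. A patient normal at that panel has no scheduled lipid test for 20 of 24 weeks, and only early terminators have a listed exit lipid panel and urinalysis. Lipid adverse-event rates, part of the primary endpoint, may therefore be understated.

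The possible shortfall runs from none, if all onset is by week 4, to about four-fifths of 24-week cases under a constant hazard with persistent abnormalities and no other testing. The documents do not allow a single value. The trial has one arm, so the effect is on absolute rates and not on a comparison between arms. For proteinuria the finding is limited to unequal exit testing. The change is worth making because the endpoint is primary and the cost is low; the design figures are unaffected.

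**What to change.** - In section 5.4.2 and Table 7-1, add the fasting lipid panel to the day-1 blood already drawn in cycles 3 to 6. Keep the repeat-if-elevated rule.
- Give completers the section 5.4.3 lipid panel and urinalysis at the last on-drug assessment (week 24, where section 5.4.2 already lists an examination), not at the visit within a week of surgery.
- Reconcile sections 5.2.2.2, 5.4.2, 5.4.3, 7.1 and Table 7-1. This includes whether completers have an end-of-treatment visit at all, since section 7.1 and the table differ. The dose actions in Table 5-5 are not part of this change.

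**Cost.** For a completer, 4 + 1 = 5 lipid panels and one urinalysis. Four panels use existing draws; the fifth may need blood added at week 24, because section 5.4.2 is not clear that a sample is taken then. Patients would have to fast on those mornings, and there is a small laboratory cost.

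If the schedule is kept, the report should state beside the lipid and proteinuria rates that fixed lipid testing ended at cycle 2 for patients with a normal panel, that no urinalysis was fixed after screening, and that exit testing differed between early terminators and completers.

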Adverse events. The addition of everolimus to letrozole has been associated with a higher rate of dose reductions or interruptions due to adverse events (52.9%) as well as discontinuations (18.8%) compared with letrozole alone (7.6% and 9.1%, respectively) in the neoadjuvant setting⁴. Grade 1 and 2 adverse events were also more frequent in the combination arm (89.8% vs. 63.6% in the letrozole alone arm)⁴. The most frequent adverse events seen in higher frequency in the combination arm as compared to the letrozole alone group include stomatitis (36.5% vs. 6.1%), rash (20.4% vs. 7.6%), asthenia (17.5% vs. 9.8%), fatigue (12.4% vs. 4.5%), anorexia (12.4% vs. 3.8%), headache (10.9% vs. 5.3%), pruritus (13.1% vs. none), dyspnea (7.3% vs. 1.5%), pneumonitis (2.9% vs. none). Laboratory abnormalities seen in higher frequency in the combination arm as compared with the control arm include hypercholesterolemia (16.1% vs. 6.1%), thrombocytopenia (18.2% vs. 0.8%), hyperglycemia (13.1% vs. 3%), increased ALT (11.7% vs. 3.8%), anemia (11.7% vs 0.8%), and neutropenia (9.5% vs. 1.5%).

Grade 3 and 4 adverse events were also more frequent in the combination arm (22.6%) as opposed to the letrozole alone arm (3.8%). Stomatitis (2.2%), fatigue (1.5%), and pneumonitis (2.2%) were the most frequent grade 3 and 4 adverse events seen in more than 1 patients (n=137) associated with the addition of everolimus, while hyperglycemia (5.1%), increased ALT (1.5%), hypokalemia (1.5%), thrombocytopenia (1.5%) constituted the most frequent biochemical grade 3 and 4 adverse events. Serious adverse events associated with everolimus occurred in 7/137 patients: pneumonitis in three patients; pneumonia and mouth ulcers/stomatitis each in two patients; and dyspnea, neutropenia, and thrombocytopenia in one patient each. All three patient cases of pneumonitis resolved within 15 days of everolimus discontinuation. Among the placebo-treated patients, there was one serious adverse event of myocardial ischemia⁴.

Overall, safety data available from completed, controlled and uncontrolled studies indicate that everolimus is generally well tolerated at weekly or daily dose schedules. The safety profile is characterized by manageable adverse events (AEs). These AEs are generally reversible and non-cumulative.

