AST or ALT elevation Grade 4 (> 20 x ULN)*	Interrupt Everolimus administration until resolution to ≤ grade 1 (or ≤ grade 2 if baseline values were within the range of grade 2). If resolution occurs ≤ 7 days, Everolimus should be re-started at one dose level lower. If resolution takes > 7 days, discontinue Everolimus.
Recurrence of grade 4 after dose reduction or toxicity requiring Everolimus interruption for > 28 days	Discontinue Everolimus.
Intolerable grade 2 mucositis, or grade 3 AE, except hyperglycemia or hypertriglyceridemia or hypercholesterolemia (see Section5.2.2.1)	- Interrupt Everolimus administration until resolution to ≤ grade 1 or baseline grade / value. If resolution occurs within ≤ 7 days, Everolimus should be re-started at the dose level prior to interruption. - If resolution takes > 7 days, or if event recurs within 28 days, hold Everolimus until recovery to ≤ grade 1 or baseline grade / value and reintroduce Everolimus at one dose level lower, if available (for this trial if it was 2.5 mgs, then therapy will be discontinued). - Patients will be withdrawn from the study if they fail to recover to ≤ grade 1 or baseline grade / value within 28 days.
Any other grade 4	Hold Everolimus until recovery to grade ≤ 1 or baseline value Reintroduce Everolimus at one dose level lower, if available (for this trial if it was 2.5 mgs, then therapy will be discontinued).
Grade 3 or 4 clinical liver failure (asterixis or encephalopathy/coma)	Discontinue Everolimus
Recurrence of intolerable grade 2 mucositis or grade 3 event after dose reduction	Reduce dose to the next lower dose level, if available. The lowest possible dose level of Everolimus is 2.5 mg daily. Below this level, Everolimus must be discontinued. If toxicity recurs at Grade 3, consider discontinuation
Recurrence of grade 4 after dose reduction	Discontinue Everolimus
Any non-hematologic toxicity requiring Everolimus interruption for > 28 days	Discontinue Everolimus

* Should HCV flare be confirmed, the guidelines for flare must take precedence (please refer to Tables 5-7 and 5-8)

Table 5-3: Dosing guidelines for Everolimus-related hematologic toxicities (see 4.2)

Toxicity	Action
Grade 2 thrombocytopenia (platelets <75, ≥ 50x10 ⁹ /L)	No action

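### Everolimus dosing tables: grade 3 hyperglycemia is referred to the stomatitis section and has no graded action, and Tables 5-2 and 5-5 disagree on grade 4 lipid events

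*Combined protocol and SAP*

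**What the plan says.** Four places in the protocol bear on this.

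- **Table 5-2 (Section 5.2.2), grade 3 row.** The row that interrupts everolimus applies to "Intolerable grade 2 mucositis, or grade 3 AE, except hyperglycemia or hypertriglyceridemia or hypercholesterolemia (see Section5.2.2.1"). Section 5.2.2.1 is the section on stomatitis, oral mucositis and mouth ulcers. It says nothing about glucose or lipids.
- **Section 5.2.2.2 and Table 5-5.** The section heading names hyperlipidemia and hyperglycemia. For glucose, the text recommends fasting measurements before and during treatment, more often with other drugs that may raise glucose, and good control before everolimus starts. The sentence that calls in Table 5-5 names hyperlipidemia and hypertriglyceridemia only. The table's title is "Management of hyperlipidemia/hypertriglycemia associated with everolimus".
- **Grade 4.** Table 5-5 says "Discontinue everolimus and treat with appropriate medical therapy". The Table 5-2 row for any other grade 4 event says "Hold Everolimus until recovery to grade ≤ 1 or baseline value Reintroduce Everolimus at one dose level lower, if available". That row carries no exception for metabolic events.
- **Section 5.4.2.** The lipid panel entry sends the reader to 5.2.2.2, not 5.2.2.1, for hyperlipidemia and hyperglycemia.

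**The concern.** Table 5-2 and Table 5-5 are operative dosing text. An investigator who follows the exception for grade 3 hyperglycemia reaches the wrong section. One who then finds 5.2.2.2 still has no everolimus action by grade. For grade 4 hypercholesterolemia or hypertriglyceridemia, two tables apply and they differ on whether everolimus may be restarted.

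The primary endpoint is the MTD, the RP2D and adverse event rates. Hyperglycemia is not among the exceptions in 4.1.1(a), so a grade 3 case meets the dose-limiting toxicity definition. If everolimus handling after such an event varies from patient to patient, or depends on which table was consulted, so does the exposure behind the reported adverse event rates and the tolerability conclusion.

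**Working it through.** **Setting the passages side by side**

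| Event | Table 5-2 | 5.2.2.2 / Table 5-5 | Result |
|---|---|---|---|
| Grade 3 lipid | Excepted; pointer to 5.2.2.1 | Interrupt, then a lower dose | One action, wrong pointer |
| Grade 3 hyperglycemia | Excepted; pointer to 5.2.2.1 | Monitoring and pre-treatment control only | No graded action |
| Grade 4 lipid | Hold, then one level lower | Discontinue | Two instructions |
| Grade 4 hyperglycemia | Hold, then one level lower | Not named | One action |

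The last row assumes that Table 5-5 is for lipids, as its calling sentence says. If the sponsor meant it to cover hyperglycemia as well, the grade 3 gap closes, but the grade 4 conflict then extends to hyperglycemia.

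**Scale**

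Inputs:
- Section 5.2.2 on the neoadjuvant letrozole plus everolimus arm: "while hyperglycemia (5.1%), increased ALT (1.5%), hypokalemia (1.5%), thrombocytopenia (1.5%) constituted the most frequent biochemical grade 3 and 4 adverse events".
- The same section on clinical events and the denominator: "Stomatitis (2.2%), fatigue (1.5%), and pneumonitis (2.2%) were the most frequent grade 3 and 4 adverse events seen in more than 1 patients (n=137").
- Section 4.3: 26 to 38 patients anticipated.

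Step 1, reproduce the stated rates as counts out of 137:
- hyperglycemia 7/137 = 5.11%
- stomatitis and pneumonitis 3/137 = 2.19% each
- fatigue, ALT, hypokalemia and thrombocytopenia 2/137 = 1.46% each

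All match the stated figures. Hyperglycemia is the highest grade 3-4 rate listed for that arm, once the separate clinical and biochemical lists are compared.

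Step 2, exact (Clopper-Pearson) 95% interval for 7/137: 2.1% to 10.2%.

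Step 3, if the rate p carries over, the expected number of cases is N × p and the chance of at least one is 1 − (1 − p)^N:

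| N | Expected at 7/137 | Chance at 7/137 | Chance over 2.1% to 10.2% |
|---|---|---|---|
| 26 | 26 × 0.0511 = 1.3 | 1 − (130/137)^26 = 74% | 42% to 94% |
| 38 | 38 × 0.0511 = 1.9 | 1 − (130/137)^38 = 86% | 55% to 98% |

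The 5.1% pools grades 3 and 4, and the gap is at grade 3. At each assumed rate these chances are therefore upper figures for grade 3 alone. Section 5.2.2 gives no grade 4 lipid rate for that arm, so the second conflict is not quantified.

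**The case against.** The strongest reply is that the protocol is not silent overall. The text before Table 5-2 says clinical judgment should guide each patient's management. Section 5.3 leaves reductions, holds and delays to the treating physician. Section 5.3.2 allows everolimus reduction at physician discretion in phase II. Section 5.6 lets the principal investigator stop treatment for a persistent grade 3 or 4 event. Section 3.3.13 requires close glucose monitoring in patients with known impaired fasting glucose or diabetes. This stands, and it rules out one tempting inference, that everolimus continues unchanged through grade 3 hyperglycemia. No passage says so; the action is unspecified and left to judgment. Discretion does not repair a wrong cross-reference, however, or settle a disagreement between two tables.

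On grade 4 lipids, both tables stop everolimus at once and differ only on reintroduction, so it would be too much to call the instructions opposite. The word *other* in the Table 5-2 row could also be read as excluding events with their own guidance. But Table 5-2 names other tables only for pneumonitis and hepatitis, and its metabolic exception sits only in the grade 3 row. The conflict therefore stands as written, though the intended reading is arguable.

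The dose-limiting toxicity definition governs cohort escalation, not an individual patient's dose. It does not contradict the dosing tables; it shows only that the unspecified event can bear on the primary endpoint.

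**Conclusion.** Three defects hold on the text: a wrong cross-reference in Table 5-2, no graded everolimus action for grade 3 hyperglycemia, and a discontinue-versus-reintroduce mismatch for grade 4 lipid events. They should be corrected.

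Several stronger readings are not supported:

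- A reader might infer that one event can lead to unchanged dosing, interruption or permanent stop. No single event gets all three.
- A reader might infer that hyperglycemia has no action at any grade. Grade 4 falls under the general grade 4 row of Table 5-2.
- A reader might take grade 3 hyperglycemia to be the leading severe event with everolimus generally. The ranking is for pooled grades in one trial. In the exemestane trial in Section 2.1.3, stomatitis (8%) and anemia (6%) exceed hyperglycemia (4%), with no grade stated.
- A reader might fear that the odd term in the Table 5-5 title will be read as hyperglycemia. The calling sentence says hypertriglyceridemia, so this is a wording slip to correct rather than a demonstrated misdirection.
- A reader might see a conflict in lipid treatment starting at grade 2 in the text and at grade 1 in Table 5-5. The text names specific drug classes from grade 2 and the table speaks only of appropriate therapy, so this is weak.

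The 74% to 86% assumes that the cited rate carries over. That trial treated for 4 months and this one plans 24 weeks, with TRC105 and its methylprednisolone premedication added; the documents give no figure for the effect of these differences. The 42% to 98% range reflects only sampling error in 7/137. The textual defects do not depend on these figures.

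**What to change.** 1. In Table 5-2, correct the reference in the grade 3 row from 5.2.2.1 to 5.2.2.2.
2. Correct the title of Table 5-5, also in the list of tables, and state whether the table covers hyperglycemia.
3. Reconcile Tables 5-2 and 5-5 and Section 5.2.2.2 so that grade 3 hyperglycemia and grade 4 lipid events each have one everolimus instruction. If Table 5-5 is declared to cover hyperglycemia, grade 4 hyperglycemia must be reconciled in the same way.

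The choice of action is the sponsor's. The cost is wording in one amendment, with no added patients or procedures.
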